Title	A Phase II study of Sorafenib and Yttrium-90 glass microspheres for Advanced Hepatocellular Carcinoma, BCLC Stage C
Clinical study phase	Phase II
Study objective(s)	
The objective of this study is to evaluate the safety of continuous sorafenib 400 mg twice daily followed, after 4 (+/-1 week) weeks, by one Yttrium-90 treatment in patients with Child-Pugh A, BCLC-stage C HCC.
 
Primary objective:
 
 • Median progression-free survival (PFS) 
Secondary objectives:
 
 • Overall Survival (OS) • Time to radiographic progression (TTRP) • To evaluate the safety of the combination of sorafenib and Yttrium-90; Adverse events (NCI-CTAE v 4.0) 
Other objectives:
 
Predictive Biomarkers of response to therapy and survival: will assess pre-treatment plasma level of IGF-1 as above, and assess its predictive ability of TTP and OS

Indication	Advanced HCC
Study design	This is a single-arm phase II clinical trial. The treatment period will be divided into 4 week cycles. During the study period, patients will undergo evaluation for safety every 4 weeks. Tumor evaluations will be performed every 8 weeks.
Type of control	None
Number of subjects	20
Primary Endpoint	To evaluate the safety of the combination of sorafenib and Yttrium-90; Adverse events (NCI-CTAE v 4.0)

Diagnosis and main criteria for inclusion

- Patients >18 years of age
- Patients with histological or cytologically documented HCC (Documentation of original biopsy for diagnosis is acceptable if tumor tissue is unavailable) *or* clinical diagnosis by AASLD criteria in cirrhotic subjects is required. For subjects without cirrhosis, histological confirmation is mandatory.
- Patients must have at least one tumor lesion that can be accurately measured in at least one dimension according to RECIST
- The target lesion has not been previously treated with local therapy (such as surgery, radiation therapy, hepatic arterial therapy, chemoembolization, radiofrequency ablation, percutaneous ethanol injection or cryoablation).
- Patients who have received local therapy, such as surgery, radiation therapy, hepatic arterial embolization, chemoembolization, radiofrequency ablation, percutaneous ethanol injection or cryoablation are eligible if the previously treated lesions have progressed or recurred can be identified as target lesions. Local therapy must have been completed at least 4 weeks prior to the baseline scan.
- Patients who have received Yttrium-90 microspheres are not eligible.
- Patients who have an ECOG PS ≤ 1
- Patients who are categorized under BCLC-C stage
- Cirrhotic status of Child-Pugh class A. Child-Pugh status should be calculated based on clinical findings and laboratory results during the screening period.
- The following laboratory parameters:
 - Platelet count $\geq 60 \times 10^9/L$
 - Hemoglobin ≥ 8.5 g/dL
 - Total bilirubin ≤ 2.5 mg/dl
 - Alanine transaminase (ALT) and AST ≤ 5 x upper limit of normal
 - Serum creatinine ≤ 1.5 x the upper limit of normal
- Prothrombin time (PT)-international normalized ratio (INR) ≤ 2.3 or PT ≤ 6 seconds above control.

Plan for statistical analysis	
The primary analysis is to evaluate the toxicity profile, and the secondary analysis to assess the overall survival and progression-free survival. The study will be monitored for toxicity. Being descriptive in nature, this trial will not focus on hypothesis testing. Descriptive statistics will be computed for all continuous and categorical variables of interest. All statistical analyses will be performed using SAS (version 9.3; SAS Institute, Inc., Cary, NC). For the primary analysis, all patients received treatment will be included the analysis for toxicity. Continuous parameters will be summarized using descriptive statistics, such as number of patients, mean, standard deviation, median and range. The toxicities will be summarized with frequency and 95% confidence interval (95% CI) by type, severity and their relationship to the treatment. Assuming a 30% of grade 3 or 4 treatment related toxicity rate, with 20 patients, the 95% CI will be (9.9%, 50.1%).
 
For the secondary analysis, the Kaplan-Meier method will be applied to estimate the probabilities of overall survival and progression-free survival as well as the median OS duration and PFS duration. The Log rank test will be used to compare the two time-to-event outcomes between patient subgroups.

--------------------------------------	---

Imaging Requirements

- Triple Phase CT – To determine liver volume measurement, identify hepatic vascular anatomy to determine TheraSphere dosimetry
 - Spiral CT abdomen/pelvis –performed with cuts of 10 mm or less in slice thickness contiguously in the axial plane to assess hepatic and extra-hepatic lesions according to the RECIST 1.1 criteria.
 - Spiral CT Chest –performed with cuts of 10 mm or less in slice thickness contiguously in the axial plane to assess extra-hepatic lesions according to the RECIST 1.1 criteria.
 - MRI can replace CT scans; however, the same imaging modality should be used for all images in an individual patient throughout the study
 - Images for efficacy assessments will require a duplicate set of images in DICOM format
 - Hepatic angiography and ^{99m}Tc -MAA– selective celiac and superior mesenteric arteriograms are needed to evaluate the hepatic arterial anatomy for the whole liver, as well as evaluation of potential sources of extra-hepatic blood supply to tumors. Repeat ^{99m}Tc -MAA may be needed to estimate cumulative lung shunt or re-asses GI flow.
-

Biomarker Variables

In addition to assessing the baseline plasma IGF-1 level, we will run exploratory biomarker studies utilizing available blood and plasma. A blood sample will be obtained from all patients at Screening. Plasma samples for biomarker evaluation will be obtained from all patients at six independent time points: (1) Screening; (2) Cycle 1/Day 1; (3) Cycle 2/Day 1; (4) Cycle 3/Day 1; (5) Pre-Yttrium-90, on the same day; and (6) End of Treatment. Plasma from patients on treatment days will be obtained from blood samples harvested prior to drug administration. These biomarker studies are optional and donation of biomarker samples is not required for participation in the clinical trial.

The planned biomarker study is designed to measure the correlation between plasma IGF-1 as a surrogate for the liver reserve, with TTRP, OS and PFS of patients, since the status of the underlying liver disease independently affect patients' survival and outcome.

Data from this biomarker analysis may be correlated with various other data obtained in this study (e.g., clinical activity, toxicity).

Table of contents

Title page	1
Protocol Synopsis.....	4
Table of contents.....	9
1.1 Background and Rationale	13
1.2 Sorafenib	14
1.2.1 Preclinical	14
1.2.2 Clinical experience	14
2. TheraSphere.....	15
2.1 General Device Description	15
2.3 Rationale for the Treatment of Hepatocellular Carcinoma.....	16
3. Study objectives.....	18
4. Study design.....	19
5. Study population.....	19
5.1 Eligibility.....	19
5.1.1 Inclusion criteria	20
5.1.2 Exclusion criteria.....	21
5.1.3 Excluded therapies and medications, previous and concomitant	22
5.2 Withdrawal of subjects from study	23
6. Treatment[s].....	24

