Additionally, we have accrued 20 patients on the current study with a primary aim to evaluate the safety of the combination of sorafenib and Yttrium-90; adverse events (NCI-CTAE v 4.0) and found no grade 4 or 5 reactions. A few grade 3 reactions occurred in the form of: liver enzymes increase (ALT=1 patient, AST=3 patients, and bilirubin = 1 patient), Fatigue (=2), and 1 patient for each of the following: encephalopathy, hypertension, hyponatremia, hypophosphatemia, thrombocytopenia, maculo-papular rash, weight loss and vomiting.

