For those patients without the pre-treatment high risk factors noted above, TheraSphere is very well tolerated, with treatment in the US commonly administered in an outpatient setting. Hospitalization for treatment effects associated with TheraSphere administration is rare.

3. Study objectives

The objective of this study is to evaluate the safety of continuous sorafenib 400 mg twice daily followed, after 3-5 weeks, by Yttrium-90 treatment in patients with child-Pugh A, BCLC-stage C HCC.

Primary objective:

- Median progression-free survival (PFS)

Secondary objectives:

- Overall survival (OS)
- Time to radiographic progression (TTRP)
- To evaluate the safety of the combination of sorafenib and Yttrium-90; Adverse events (NCI-CTAE v 4.0)
-

[figure not shown]
Other objectives:

Predictive Biomarkers of response to therapy and survival: will assess pre-treatment plasma level of IGF-1 as above, and assess its predictive ability of TTP and OS

4. Study design

This is a single-arm phase II clinical trial to evaluate the safety of continuous sorafenib at 400 mg twice daily followed, after 4 (+/- 1 week) weeks from starting sorafenib, by Yttrium-90 treatment concomitant with sorafenib, in patients with child-Pugh A, BCLC-stage C HCC. Of note, the time between starting sorafenib and Yttrium-90 administration will be 4 weeks regardless whether the patient underwent dose reductions or interruptions. Patients will continue taking the maximum tolerating dose of sorafenib, with no interruption during and after the Yttrium-90 procedures. This is a single-institution study that will be conducted at MDACC, Department of GI Medical Oncology and Department of Interventional Radiology. No sorafenib interruptions around the procedure will be applied, and only one Y-90 treatment only will be performed.

Study schema:

5. Study population

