8.1 Statistical and analytical plans

Statistical consideration for 2012-0870: study of sorafenib plus theraspheres for extrahepatic hepatocellular carcinoma (redesign, 20 patients have enrolled in study 2012-0870)

This is a phase II study of sorafenib plus theraspheres for extrahepatic hepatocellular carcinoma (EHC). The primary objective is to evaluate the progression-free survival (PFS), where the progression-free survival will be measured from the start of therapy until failure to disease progression or death.

Historical data showed that the median PFS was 4.1 months for EHC patients treated with sorafenib alone. We expect that the combination treatment would improve the PFS. A maximum of 40 will be recruited for the study at a rate of 1-2 patients per month. The study will monitor toxicity and futility.

Futility monitoring

The primary endpoint PFS will be monitored using the method of Thall et al. (2005), and we will stop enrolling patients to the study if, based on the available data, we have little reason to believe that the median PFS of the combination therapy (m_E) is more than that of sorafenib alone (m_S) in the historical data, which was 4.1 months. Formally, we'll stop the study early if

$$\text{Prob}(m_E > m_S | \text{data}) < 0.15$$

That is, if there is less than 15% chance the median PFS of the combination therapy is more than that of sorafenib, the trial will be stopped. Where m_S represents the median PFS for sorafenib alone in the historical data with an inverse gamma distribution $IG(11, 41)$, which corresponds to a mean of 4.1 months and a variance of 1.87. m_E represents the median PFS for the study combination therapy, assuming the prior for m_E is $IG(2.17, 4.8)$, which has the same mean as m_S but with a much larger variance (i.e. 99) to reflect much greater uncertainty about the median PFS of the combination therapy of sorafenib and theraspheres.

Futility monitoring will start once 20 patients have been enrolled. Assuming an accrual rate of 1.5 per month and an additional follow-up of 12 months, the operating characteristics for the futility stopping rule under various true states are summarized in the following table 8, with results based on 5000 simulations.

Table 8. Operating characteristics for the time-to-progression monitoring

True Median Time to progression	Pr(stop early)	Average Number of Patients Treated (25th, 75th percentiles)
2	0.993	21 (20, 20)
3	0.529	31.4 (20, 40)
4	0.100	38.3 (40, 40)

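### The synopsis still gives a 20-patient, toxicity-primary design, while Section 8.1 has PFS primary, a maximum of 40 and interim stopping rules that Section 8.2 says do not exist

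*Combined protocol and SAP*

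**What the plan says.** **Synopsis.** The number of subjects is 20. The primary endpoint row reads "To evaluate the safety of the combination of sorafenib and Yttrium-90", assessed by adverse events. The statistical plan says "The primary analysis is to evaluate the toxicity profile, and the secondary analysis to assess the overall survival and progression-free survival", calls the trial descriptive, and adds "The study will be monitored for toxicity". Its precision statement is "Assuming a 30% of grade 3 or 4 treatment related toxicity rate, with 20 patients, the 95% CI will be (9.9%, 50.1" percent). Yet the objectives row of the same synopsis lists "Median progression-free survival (PFS") as the primary objective and safety as a secondary one.

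**Sections 1.1, 3 and 4.** Section 1.1 reports that "we have accrued 20 patients on the current study with a primary aim to evaluate the safety". Section 3 names median PFS as the primary objective, under a lead sentence about safety. Section 4 opens with "This is a single-arm phase II clinical trial to evaluate the safety of continuous sorafenib".

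**Section 8.1.** This is marked "redesign, 20 patients have enrolled in study 2012-0870". It makes PFS the primary objective and recruits at most 40 patients. Futility monitoring starts at 20 enrolled. Toxicity monitoring, which the section itself calls interim, starts at 20 evaluated patients and repeats after each further 5. Toxicity is analysed as secondary, with a 90% credible interval.

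**Sections 8.2 and 8.3.** The whole entry under planned interim analyses in 8.2 is that there are none. Section 8.3 refers the sample size to 8.1.

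**The concern.** Sample size and primary endpoint are the two items a protocol most needs to state once. Here each is stated twice, in current text. A reader who takes the row labelled as the primary endpoint, together with the synopsis analysis plan, gets a different primary analysis from a reader of Section 8.1. Section 1.1 shows that the toxicity results of the first 20 patients were already known when this version was written. Until the text is consistent, either toxicity or PFS could later be cited as the prespecified primary.

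The size matters in its own right. At the synopsis figure of 20, accrual is already complete. Under Section 8.1, 20 is only the point at which monitoring begins, and the operating characteristics in Tables 8 and 10 apply to a maximum of 40.

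Section 8.2 is where a reader looks for planned looks at the data. It lists none, although Section 8.1 can stop the trial on two separate rules.

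**Working it through.** The question is whether one set of figures is simply wrong, or whether two designs sit side by side.

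**1. Reproduce the synopsis interval.** Inputs from the synopsis: p = 0.30, n = 20, 95% level. Wald interval: p ± 1.96 × √(p(1 − p)/n).
- n = 20: √(0.21/20) = 0.1025; half-width 0.201; interval 9.9% to 50.1%. This matches the synopsis.
- n = 40: √(0.21/40) = 0.0725; half-width 0.142; interval 15.8% to 44.2%.

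The synopsis figure is correct arithmetic, tied to 20 patients.

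**2. Reproduce the toxicity rule in Section 8.1.** Inputs: prior beta(0.6, 1.4); stop if Pr(θ > 0.30 | data) > 0.85; looks at 20, 25, 30 and 35 patients. With x toxicities in n patients the posterior is beta(0.6 + x, 1.4 + n − x).

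| n | Table 9 boundary | Posterior probability at the boundary | At one fewer |
|---|---|---|---|
| 20 | 9 | 0.906 | 0.807 |
| 25 | 11 | 0.918 | 0.838 |
| 30 | 12 | 0.863 | 0.764 |
| 35 | 14 | 0.883 | 0.801 |

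All four boundaries are the smallest counts that cross 0.85.

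Exact binomial early-stopping probabilities over those four looks, with a maximum of 40:

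| True rate | Computed | Table 10 |
|---|---|---|
| 0.1 | 0.0001 | 0.0001 |
| 0.2 | 0.0168 | 0.017 |
| 0.3 | 0.2114 | 0.211 |
| 0.4 | 0.6512 | 0.651 |
| 0.5 | 0.9377 | 0.938 |

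**3. Check the futility rule.** A simulation with exponential event times, 1.5 patients per month and 12 months of further follow-up (1,500 replicates) gave early-stopping probabilities of 0.993, 0.528, 0.090 and 0.016 for true medians of 2, 3, 4 and 5 months. Table 8 gives 0.993, 0.529, 0.100 and 0.017. Table 8 too describes a trial with a maximum of 40.

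**4. Toxicity interval on the terms of Section 8.1.** This takes an observed rate of 30%, which is an illustration and not a planned count.

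| Data | Posterior | 90% credible | 95% credible |
|---|---|---|---|
| 6/20 | beta(6.6, 15.4) | 15.4% to 46.7% | 13.2% to 50.2% |
| 12/40 | beta(12.6, 29.4) | 19.1% to 42.0% | 17.3% to 44.5% |

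**5. Set the statements side by side.**

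| Item | Synopsis rows left unchanged | Section 8.1 |
|---|---|---|
| Patients | 20 | maximum 40 |
| Primary | toxicity | PFS |
| Toxicity interval | 95% confidence | 90% credible, secondary |
| Stopping rules | toxicity monitoring mentioned, no rule | futility from 20 enrolled; toxicity at 20, 25, 30, 35 |

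The calculations are coherent within each column. The columns cannot both describe the trial, and Section 8.2 agrees with neither set of rules in the right-hand column.

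**The case against.** The best reply is that no one would be misled for long. Section 8.1 calls itself a redesign, Section 8.3 points to it, Section 1.1 explains the earlier safety aim, and the synopsis objectives row is already updated. No boundary or operating characteristic in 8.1 is wrong because of the old rows. That stands, and it is why wording is enough. But no clause gives 8.1 precedence, and the synopsis is part of the protocol.

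On Section 8.2, one can say that it directly follows the monitoring rules, and that continuous monitoring is not an interim analysis. The rules are data-driven grounds for stopping, however, and 8.1 itself describes the toxicity looks as interim. Section 10 also lists interim results among reasons to end the study, but in a generic list of examples, so it adds little.

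Several smaller points are fair:
- The interval widths show which size the synopsis figure belongs to. They do not measure harm.
- The synopsis example counts grade 3 or 4 treatment-related toxicity, while 8.1 monitors non-hematological grade 3 or greater. This is a lesser mismatch, not a rival endpoint definition.
- The safety lead sentences are incomplete rather than contradictory, since safety remains a secondary objective.
- Section 8.1 is not perfectly clean as a target: the title of Table 8 and the primary analysis paragraph speak of time to progression where PFS is meant.

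**Conclusion.** The concern holds, with high confidence, and must be fixed. The current protocol gives 20 against a maximum of 40 patients, toxicity against PFS as primary, and no planned looks against four tabulated toxicity looks plus futility monitoring from 20 enrolled. It is not an arithmetic error: the synopsis interval is right for 20 patients, and the monitoring tables in Section 8.1 are reproduced for a maximum of 40, the futility table to within simulation error. The conclusion rests on reading 8.1 as the governing plan, which its redesign label, the cross-reference in 8.3 and the PFS objective in Section 3 all support.

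**What to change.** 1. In the synopsis, state a maximum of 40 patients, PFS as the primary endpoint, and a statistical plan that matches Section 8.1: PFS primary, toxicity secondary, Bayesian monitoring and analysis. Say whether the 40 includes the 20 already enrolled; looks starting at 20 imply it, but no sentence says so. Section 8.1 already supplies a precision statement for PFS (a 95% credible interval of 2.76 to 6.08 months at 25 events and a median of 4.1 months), which the synopsis could carry.
2. Bring the safety-only lead sentences in the synopsis objectives and Sections 3 and 4 into line with the PFS primary objective. Use PFS consistently in the title of Table 8 and the primary analysis paragraph.
3. Replace the 20-patient toxicity precision statement with one that uses the toxicity event and interval of Section 8.1, for example a 90% credible interval of 19.1% to 42.0% if 12 of 40 patients have the event.
4. In Section 8.2, replace the present entry with a reference to the two rules in 8.1: futility from 20 enrolled, and toxicity at 20 evaluated and then after each cohort of 5.

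The cost is amendment wording. No patients, visits, looks or analyses are added.

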ECOG	Eastern Cooperative Oncology Group
eCRF	Electronic Case report Form
EGFR	Epidermal growth factor receptor
ERK	Extracellular Signal-regulated Kinases
FACT-Hep	Functional Assessment of Cancer Therapy – Hepatobiliary Questionnaire
FHSI8	Functional Assessment of Cancer Therapy – Hepatobiliary Symptom Index 8
FDA	Food and Drug Administration (US)
FLT3	FMS-like tyrosine kinase 3
GBq	Giga Becquerel
GCP	Good Clinical Practice
GI	Gastrointestinal
GMP	Good Manufacturing Practice
Gy	Gray, a measure of irradiation dose
HCC	Hepatocellular Carcinoma
HDE	Humanitarian Device Exemption
HFSR	Hand foot skin reaction
IB	Investigator’s Brochure
ICF	Informed Consent Form
IDMC	Independent Data Monitoring Committee
INR	International Normalized Ratio for prothrombin time
IR	Immediate release
IRB	Institutional Review Board
LFT	Liver function tests
MAPK	Mitogen Activated Protein Kinase
MEK	MAP Kinase / ERK Kinase 1
NCI	National Cancer Institute
NM	Nano molar

NYHA	New York Heart Association
PDGFR	Platelet Derived Growth Factor Receptor
PE	Physical exam
PFS	Progression free survival
PT	Prothrombin Time
PTT	Partial thromboplastin time
RCC	Renal cell carcinoma
RECIST	Response Evaluation Criteria in Solid Tumor
SAE	Serious adverse event
99mTc-MAA	Technetium-99m Macro-aggregated albumin
TS	TheraSphere
TTP	Time-to-Progression
SUSARs	Suspected unexpected serious adverse reactions
UADE	Unanticipated Adverse Device Event
VEGF	Vascular Endothelial Growth Factor
VEGFR	Vascular Endothelial Growth Factor Receptor
WBC	White Blood Cells
Y-90(Y-88, Y-91)	Yttrium-90 and isotopes

1 Introduction

More than 80% of hepatocellular carcinoma (HCC) patients are not candidates for curative treatments, such as resection or liver transplant, the outcome of HCC patients remained very poor. Recently, sorafenib—a multitarget tyrosine kinase inhibitor—was found to improve survival of patients with Child-Pugh A unresectable HCC. The median overall survival (OS) was 10.7 months for patients on sorafenib vs 7.9 months for placebo, $P = .0006$, and median time-to-progression (TTP) was 5.5 months for patients on sorafenib vs 2.8 months for placebo, ($P < 0.001$). Notably, out of all patients under the SHARP trial, 421 patients had extrahepatic spread (EHS) and/or macrovascular invasion (MVI) (Sorafenib=209, placebo=212). For patients with EHS and/or MVI (Sorafenib vs placebo), OS was 8.9 vs 6.7 months (HR: 0.77; 95% CI: 0.60, 0.99) and TTP was 4.1 vs 2.7 months (HR: 0.64; 95% CI: 0.48, 0.84). (Sherman M, et al. 44th ASCO Annual Meeting).

Considering that the cause of death of HCC patients with extrahepatic spread is mainly intrahepatic HCC progression or hepatic failure, rather than extrahepatic metastasis, the intentional addition of an intra-arterial local therapy modality, such as

Yttrium-90 microspheres, could offer added survival and quality of life benefit.
Surprisingly, no data have been available on this approach until now.

1.1 Background and Rationale

TheraSphere[®], a localized, minimally embolic therapy, capitalizes on the hypervascularity nature of tumors delivering Yttrium-90 microspheres, a source of beta energy, via the hepatic artery to the tumor bed. The distribution of blood flow is 3 to 7 times greater within the tumor than the surrounding noncancerous tissue. Consequently, there is preferential delivery of microspheres to the tumor capillary bed allowing for higher doses of radiation to be delivered to the tumor relative to the surrounding non-tumor parenchyma. The ability to concentrate radioactive microspheres within the tumor leads to an "inside-out" radiation, which in turn exerts a local tumoricidal effect.

Preliminary data: Treatment details were retrospectively collected for a cohort of patients with advanced multifocal HCC at MD Anderson Cancer Center between January 2008 & May 2010 who received systemic sorafenib followed by liver directed therapy with Yttrium-90 microspheres. 19 patients met the criteria (BCLC stage B=3 patients, and BCLC stage C=16 patients), (Child-Pugh A=16, and Child-Pugh B=3). Response rate was: PR 21% (n=4) and 79% (n=15) of these patients had SD by RECIST criteria. Median TTP per liver tumors was 7.3 months, and OS was 10.3 months. Grade 3 /4 hepatic toxicities were absent within 30 days post Y90 microsphere therapy. Significant adverse events were: GI ulcer (1), pancreatitis (1), lymphopenia (1), and mucositis (2) from which all patients recovered uneventfully.

It will be also important in the future to determine how to most effectively integrate molecular assays that assess the likelihood of therapeutic benefit into clinical practice. Therefore, we plan to assess potential biological markers candidates to help predict response or survival benefit to this approach. Insulin like growth factor-1 (IGF-1) is produced predominantly in the liver, and our recent study showed that pre-treatment plasma IGF-1 may correlate with patients' survival, and hence improve the prognostic ability of the Cancer of the Liver Italian Program (CLIP) score, and Barcelona Clinic Liver Cancer (BCLC) staging. IGF-1 significantly correlated with the clinicopathologic features. With an optimal IGF-1 cut point of 26 ng/mL, the overall survival for patients with IGF-1 >26 was 17.7 months (95% CI of 13.6, 22.8), and for IGF-1 ≤ 26 (60/288 patients) was 5.8 months (95% CI of 4.0, 12.5), p-value<0.0001.

Additionally, we have accrued 20 patients on the current study with a primary aim to evaluate the safety of the combination of sorafenib and Yttrium-90; adverse events (NCI-CTAE v 4.0) and found no grade 4 or 5 reactions. A few grade 3 reactions occurred in the form of: liver enzymes increase (ALT=1 patient, AST=3 patients, and bilirubin = 1 patient), Fatigue (=2), and 1 patient for each of the following: encephalopathy, hypertension, hyponatremia, hypophosphatemia, thrombocytopenia, maculo-papular rash, weight loss and vomiting.

